American Heart Association and Neurocritical Care Society Guidelines for the management of ICH. This will include, but not be limited to, serial clinical and paraclinical evaluations including CT scans, metabolic profile, echocardiography, etc. Current standards-of-practice, including euvolemia targets, electrolyte replacement, venous thrombosis prophylaxis, normoglycemia, etc. will be maintained in this population. The risks most commonly seen with conivaptan use are hypotension (associated with volume loss), site reactions, and electrolyte abnormalities including hypokalemia and hypomagnesemia that may result in dysrhythmia. Thus, patients will be closely monitored for these and other problems. Finally, to evaluate for any unforeseen problems with the use of this medication, these patients will receive standard of care practice, including neuroimaging and outpatient clinic follow-up.

The seven patients in this study will receive 40mg/day of the study medication conivaptan. In this early phase study, our focus will be to assess the safety and tolerability of this medication. The available clinical data on conivaptan in the neurocritical care population suggest the potential harm is negligible. Data in TBI patients demonstrate conivaptan is safe and well tolerated using a single dose (20mg) to increase Na⁺ in a controlled fashion to reduce ICP (Galton et al., 2011). Previous work has demonstrated the safety and tolerability of conivaptan, in doses ranging from 20-80mg/day, in the neurocritical care population (Murphy et al., 2009; Wright et al., 2009; Naidech et al., 2010; Dhar & Murphy-Human, 2011). Conivaptan has been demonstrated to be safe and effective in lowering ICP, and increasing serum sodium, in the neurocritical care population (Murphy NCC '09, Wright NCC '09, Dhar NCC '11, Galton NCC '11). Also noted have been improvements in CPP and stable blood pressure, and a prolonged reduction in ICP. Finally, the method of intermittent bolus dosing of conivaptan is equally effective in raising and maintaining serum sodium in the neurocritical care population as continuous infusion, with potentially less risk of adverse reactions including phlebitis (Murphy NCC '09, Wright NCC '09).

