6.9 Primary Assessments (Safety and Tolerability)

Conivaptan was approved by the FDA in 2005 for the treatment of euvolemic and hypervolemic hyponatremia in a hospitalized setting using doses of 20-40mg/day. In the 11 years it has been on the market, numerous studies using it at doses ranging from 20-80mg/day have been done furthering the data on its effect on hyponatremia (National Monograph, 2006; Ghali et al., 2009; Zeltser et al., 2007; Verbalis et al., 2008; Annane et al., 2009; Human et al., 2012; Marik & Rivera, 2013), as well as studies showing its lowering of ICP in patients with TBI (Dhar & Murphy-Human, 2011; Galton et al., 2011). These benefits should relate to a decrease in CE.

In all these studies, conivaptan was well tolerated and safe, with no drug-related serious adverse events observed. For example, in the Ghali et al (2009) study, no deaths were study related, and the side effects of headache, hypotension, nausea, and constipation occurred most frequently. Based on these observations, we expect only minimal, if any, side effects in our study, since we are using a dose (40mg/day) which is lower than the 80mg/day used in several of the above mentioned studies. And, we feel there are no special concerns in the patient population included in our study (non-traumatic ICH) since conivaptan has already been safely used in TBI ICH patients.

An evaluation of the safety assessment parameters of each of the seven (7) subjects will be done by the PI and Co-I during the patient's care. Should events occur regarding the administration of conivaptan that raise safety concerns, the PI has the authority to withdraw the subject and/or halt the study pending further investigation.

Specific safety assessment parameters will include the following-

- **Neurologic tolerability:**
 1. Seizure frequency (15-20% of patients with ICH have seizures associated; EEGs will be used and measured; all treatments will be the same, using anti-seizure drugs).
 2. Total Na+ mEq received.
 3. ICP variability. In all patients for whom ICP is monitored, the hourly mean and median ICP will be compared. Further, patients will be graphed and the area-under-the-ICP-curve and above 10, 15, and 20 mmHg will be calculated and averaged to provide a more continuous comparison.
 4. ICP response to osmotic therapy. In patients receiving mannitol or 23.4% NaCl boluses, the average ICP reduction in the hour following administration will be compared.

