7.1 Risks and Benefits

7.1.1 Potential risks

Potential risks associated with conivaptan may include hypotension, excessive rise in serum sodium, development of central pontine myelinolysis, increase in seizure frequency, expansion of initial ICH, development of new ICH and/or stroke, development of new cardiac arrhythmia, development of pulmonary edema, change in renal function, and development of an infection.

Potential risks involving blood draws may include temporary discomfort from the needle stick, pain or bruising, lightheadedness, and infection at the site.

Potential risks of CT scans are exposure to radiation from X-rays, dizziness, cold sensation at injection site, worsening of poor kidney function, allergic reaction to injection dye, soreness or swelling at the injection site.

Potential risks will be minimized by blood pressure monitoring, monitoring of total Na⁺ mEq received, EEG monitoring and measurement (15-20% of patients with ICH have seizures, anti-seizure medications will be used), ICH/ICP monitoring, monitoring of troponin levels, chest x-ray and monitoring of pulmonary parameters (such as PO₂, FiO₂, A-a gradient), assessment of renal function by the RIFLE criteria, monitoring for infections.

Training sessions for all clinical study personnel will occur prior to the start of the study to discuss the potential risks that could occur, and the monitoring for and treatments that are in place.

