7.2 Adverse Events

An adverse event (AE) is any untoward medical occurrence in a subject administered a study procedure. An AE can therefore be any unfavorable and unintended sign (including an abnormal laboratory finding), symptom, or disease temporally associated with the use of study procedures. Since this is a study involving an FDA drug, conivaptan, used for approved purposes, exempt from IND regulations, we do not anticipate adverse events to be a common occurrence in this research study.

In case of such occurrence, for all AEs, the investigator will obtain adequate information to determine the following:

- The appropriate descriptive term
- Severity

NSJC-1601
V6APR2018

- Onset/resolution dates and outcome.
- Causality: the relationship of each AE will be defined as “unrelated” or “related” to study procedures:
Unrelated: There is little or no possibility that the study procedures caused the AE;
Related: There exists at least a reasonable possibility that the study procedures caused or contributed to the AE; an inability to identify an alternate etiology for an AE should not, by itself, justify a “related” attribution.
- Whether it meets the criteria for classification as a SAE.

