8.3 Data Sharing

- 1) The results obtained from this study will be prepared within a manuscript for submission to a peer-reviewed journal.
- 2) The results will also be used as preliminary data for future studies, including a rigorous, controlled study of the efficacy and safety of conivaptan compared to traditional treatments/a phase II dosing study.

9. Statistical Analysis

Descriptive statistics will be used to summarize the baseline characteristics and the outcomes, such as adverse events and the hospital length of stay. In addition, Mixed model with unequally spaced repeated measures will be performed to evaluate the change of the variables with unequally spaced repeated measures, such as edema content, ICH score, GCS score, and APACHE II score, where unequally spaced repeated edema content measurements for 7 patients will be plotted; while Mixed model with equally spaced repeated measures will be performed to analyze the change of the variables with equally spaced repeated measures, such Mg and PO₄.

10. Study Oversight

The PI and the research team will be responsible for all safety assessments. Safety will be assessed for all patients enrolled in an ongoing fashion based on the incidence of AEs, SAEs, and treatment discontinuations due to AE. If any significant safety issues arise, a decision to modify or terminate the trial will be made. If requested, the study will be made available for monitoring, auditing, IRB review, and regulatory inspection by providing direct access to study related source data to oversight bodies like FDA.

11. IRB Review/Ethics/Informed Consent

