- Participation in another study for ICH or intraventricular hemorrhage.
- ICH related to infection, thrombolysis, subarachnoid hemorrhage, trauma or tumor.
- Presence of HIV or active fungal infection that is known based on information in the EMR.

- Continued use of digoxin or amlodipine (as recommended by the manufacturer due to CYP3A inhibition).
- Active hepatic failure as defined by AST >160 units/L and/or ALT >180 units/L, or total bilirubin levels greater than four times normal levels (>4.8mg/dL).
- Serum Na⁺ ≥ 145 mmol/L (admission labs or any time prior to recruitment/enrollment).
- Unable to receive conivaptan based on contraindications indicated by the manufacturer.
- Pregnant or lactating females.
- Not expected to survive within 48 hours of admission, or a presumed diagnosis of brain death.

5. Statistical Methods

5.1: Study Subjects and Analysis Sets

All enrolled patients will be included in a single analysis set and data will be summarized using frequencies and percentages.

5.2: General Methodology

This study is looking to preliminarily evaluate the safety, tolerability, and efficacy of conivaptan treatment. Unfortunately, it is not powered to provide robust statistical evaluation of safety and tolerability, nor to detect differences in efficacy between subjects. As such, all analysis will be descriptive in nature. Categorical variables will be summarized using counts and percentages. Continuous variables will be summarized using descriptive statistics: number of patients, mean, median, and full range, as appropriate.

Statistical analysis will consist of:

- Descriptive analysis of patient characteristics
- Frequency of relevant complications and medical interventions
- Changes in CE volume

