5.3 Evaluation of Objectives

Safety and tolerability will be assessed via the number of patients that experience abnormal seizure activity, show abnormal laboratory values, have increased infection rates, or exhibit an adverse events directly related to treatment with conivaptan. The change in CE volume will be reported as a measure of potential efficacy, and potential impacts on cost of care will be assessed by the length of stay in the ICU and the use of medical interventions to reduce CE volumes. Patient outcomes will be assessed using the mRS at discharge. Due to the small number of patients in this trial and absence of a control group, all evaluation will be descriptive only.

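### Hypotension, the first-named conivaptan risk, reaches the primary safety evaluation only as an adverse event attributed to the drug

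*SAP*

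**What the plan says.** Three places in the protocol identify hypotension as a known effect of the drug. Section 6.7 states "The risks most commonly seen with conivaptan use are hypotension (associated with volume loss"). Section 7.1.1 opens its list with "Potential risks associated with conivaptan may include hypotension, excessive rise in serum sodium". The preamble to 6.9 says of one earlier publication that "the side effects of headache, hypotension, nausea, and constipation occurred most frequently".

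Blood pressure is among the vital signs that 8.1 collects from ICU admission to day 7, and 7.1.1 names its monitoring as a way to limit risk.

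Section 6.9 then introduces its primary measures with "Specific safety assessment parameters will include the following". The list covers neurologic, cardiac, pulmonary, renal and infectious tolerability and in-hospital mortality. The cardiac items are troponin and new arrhythmia. Neither blood pressure nor hypotension appears.

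SAP 5.3 evaluates safety and tolerability by counting patients who meet any of four criteria: seizure activity, abnormal laboratory values, infection, or a drug-attributed event. The last two read "have increased infection rates, or exhibit an adverse events directly related to treatment with conivaptan".

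Other sections are broader. Protocol section 10 assesses safety "based on the incidence of AEs, SAEs, and treatment discontinuations due to AE". Protocol section 9 summarises adverse events descriptively. SAP 5.2 plans "Frequency of relevant complications and medical interventions". SAP 5.4 defines and collects adverse events whether or not the drug caused them.

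**The concern.** Safety and tolerability is the primary objective, and hypotension is the only effect named in all three of the protocol's accounts of conivaptan's risks. One would expect the primary evaluation to measure it directly. Instead its inclusion depends on two judgements: that a fall in pressure is an adverse event at all, and that the drug was directly responsible.

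Both are hard to make here. There is no control arm. Table 1, note a, lists blood-pressure correction among the standard-of-care steps soon after arrival. Section 6.8 allows sedation and mannitol as needed, and section 3 links mannitol to swings in circulating volume. Each offers another explanation for a fall after a dose.

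The rationale also leans on this variable. The protocol and the SAP background both cite stable blood pressure in earlier patients as support for the drug, yet no named summary would show whether that holds in intracerebral hemorrhage.

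**Working it through.** The plan states no figure to reproduce, and the sample size of 7 does not come from a formula. The check sets the sections side by side.

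**Step 1: risks in 7.1.1 against outcome items in 6.9.**

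| Risk in 7.1.1 | Outcome item in 6.9 |
|---|---|
| Hypotension | None |
| Excessive sodium rise | None (sodium received is an exposure) |
| Central pontine myelinolysis | Neurologic 5 |
| Seizures | Neurologic 1 |
| Expansion of the hemorrhage | Neurologic 5 |
| New hemorrhage or stroke | Neurologic 5 |
| Arrhythmia | Cardiac 2 |
| Pulmonary edema | Pulmonary 1 |
| Renal function | Renal 1 |
| Infection | Infectious 1 |

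So 10 − 2 = 8 of the 10 risks have an item. Sodium rise is covered elsewhere: 6.8 stops dosing at 160 mmol/L or after a rise of more than 12 mmol/L in 24 hours, and SAP 5.3 counts abnormal laboratory values. Hypotension has neither a specific stopping rule nor a named measure.

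**Step 2: routes into SAP 5.3.** Hypotension is not a seizure, a laboratory value or an infection. That leaves 1 of the 4 criteria, the one that requires attribution to conivaptan.

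**Step 3: the attribution standard.** SAP 5.3 does not define a direct relationship. Protocol 7.2 defines a related event by a lower bar, a reasonable chance that study procedures played a part. It also says that "an inability to identify an alternate etiology for an AE should not, by itself, justify a" finding of relatedness. SAP 5.4 gives the decision to the principal investigator. The two documents therefore leave unclear which standard governs the primary count.

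**Step 4: what makes a fall an adverse event.** Neither document gives a pressure threshold or a treatment trigger. Protocol 7.4 relies on events that the investigator observes or the subject volunteers. Patients with a Glasgow Coma Scale of 14 or below enter through a representative and may not be able to report symptoms. A fall that nobody labels an adverse event has no named summary. SAP 5.2 promises ranges for continuous variables in general, without naming blood pressure.

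**Step 5: size.** Let h be the number of the 7 patients who become hypotensive by any cause. The number counted for hypotension under SAP 5.3 can be any whole number from 0 to h. The documents give no value for h and no rate at which events would be judged related, so nothing narrower can be derived.

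**The case against.** The strongest reply is that hypotension is already captured. SAP 5.4 includes untoward clinical signs whatever their cause and records intensity, duration, relationship and interventions. Protocol sections 9 and 10 and SAP 5.2 carry no relatedness filter. An event judged unrelated therefore leaves one count, not the whole safety evaluation. This stands, and it sets the limit of the point. It does not repair SAP 5.3, which is where the primary objective is evaluated.

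Second, the bar in Protocol 7.2 is low, and hypotension soon after a dose of a drug known to cause it might well be called related. That is possible, and it would be speculation to assert the opposite. But SAP 5.3 uses a stricter-sounding term, and the result should not turn on which standard is applied.

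Third, site reactions, headache, nausea and constipation are also named side effects without an item in 6.9. True, but each appears in only one of the three accounts.

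Fourth, with 7 uncontrolled patients and a descriptive plan, little inference is possible. This stands too, and it is why the remedy is a count and a listing, not a test.

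A reader might also infer from Table 1 that the first blood pressure after each dose is taken 6 hours later, so that brief falls would be missed. The documents do not support this. The vital-signs row sits under data collection from the medical record; note h describes it as standard-of-care information; one column spans days 3 to 6; and 6.8 leaves vital signs to the Neuro-ICU protocol. Denser readings may well exist.

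**Conclusion.** The point holds in limited form. The primary safety evaluation has no blood-pressure measure, and SAP 5.3 admits the leading expected drug effect only through a relatedness filter that cannot be applied reliably in this cohort. The conclusion rests on the text of 6.9 and SAP 5.3, and on the assumption that blood-pressure treatment, sedation or mannitol will overlap with dosing in at least some patients. The plan permits such overlap but does not say how often it will occur.

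A reader might infer that hypotension goes unrecorded or unreported, or that a particular number of cases would be lost. Neither follows: recording is complete on paper, and no event rate is given. The improvement is minor to moderate. It affects how the primary result is described, not data capture or the bedside care of patients.

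**What to change.** Add a hemodynamic item to Protocol 6.9 and SAP 5.3, covering all treated patients:

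1. The number of patients with hypotension by a definition fixed in advance, for example a mean or systolic pressure threshold, or a need for fluid or a vasopressor. Count it regardless of attributed cause, and show the principal investigator's relatedness call beside it instead of using it as a filter.
2. A per-patient listing, for each dose, of the pre-dose mean arterial pressure and the lowest value up to the next dose (up to 12 hours after the fourth), drawn from all readings in the medical record. Note any deliberate blood-pressure lowering, mannitol or sedation in the same interval.

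The cost is a few lines of text and modest extraction work: at most 7 × 4 = 28 doses and 28 × 2 = 56 listed values, plus the treatment notes. No new visit or measurement is needed. The drawbacks are coordinator time in a study with a limited budget, and an all-cause count that cannot be attributed to conivaptan without a control group and may look less favourable. It should be presented as a description of 7 patients, not as an estimated rate.

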5.4 Safety Evaluation

Subjects will be monitored throughout their hospital stay. Adverse events (AE) will be assessed in terms of their seriousness, duration, intensity, and relationship to the study drug. All

anticipated and unanticipated AE will be collected. Subjects will be able to contact the investigator at any time during the study. The outcome of each event, including any interventions used, will be observed and documented.

a. Adverse Event Definitions and Reporting Requirements

An AE is any complaint or untoward medical occurrence that is an unintended disease or injury or untoward clinical sign (including abnormal laboratory findings) in a subject, whether or not it is related to the investigational drug.

A Serious Adverse Event (SAE) is an untoward medical occurrence in a subject that may or may not be related to the investigational drug, but that meets the criteria of “serious” by resulting in one of the following outcomes:

- Death
- Requires initial or prolonged inpatient hospitalization
- Is life-threatening (that is, immediate risk of dying).
- Is a persistent or significant disability/incapacity.
- Other significant medical hazard.

All adverse events will be collected and documented throughout the study. The PI will assess each AE to determine severity, relatedness to the study drug, and if it was anticipated or unanticipated.
